7.3 SERIOUS ADVERSE EVENTS

An SAE is any AE that meets any of the following criteria:

- Results in death
- Is *life-threatening*
- Requires inpatient *hospitalization* or prolongation of existing hospitalization
- Results in persistent or significant *disability/incapacity*
- Is an *important medical event*

Sponsor Name: Woebot Health

Protocol Number: WB001-001

UNANTICIPATED ADVERSE DEVICE EFFECTS

A suspected unanticipated adverse device effect (UADE) is defined as an untoward and unintended response to a study treatment, which is not listed in the applicable product information, and meets at least one AE or SAE criterion, and is assessed as causally related to the study treatment. The Sponsor or designee will be responsible for carrying out required reporting to investigators, health authorities, and other entities as required by law.

DOCUMENTING AND REPORTING ADVERSE EVENTS AND SERIOUS ADVERSE EVENTS

Reporting of non-serious AEs and SAEs will begin at the time of first interaction with the app and will continue through EOT. Any new clinical condition or worsening of existing conditions between the time the informed consent form (ICF) is signed, and the first use of the study intervention will be recorded as AE/SAEs unrelated to the device.

AEs and SAEs may be reported spontaneously by participants, discovered as a result of general, non-leading verbal questioning by the study staff, or determined by assessments. As needed, qualified study staff will inform investigators to inquire about any new symptoms or worsening of symptoms during the telehealth visits at Weeks 4 and 8. In the interim, participants will be instructed to contact the investigator if new or worsening symptoms develop outside of key assessment visits. All incidences confirmed as AEs or SAEs will be monitored and recorded in the eCRF throughout the entire study.

The investigator must pursue and obtain adequate information about all incidences they deem as AEs and SAEs. At minimum this includes a description of the event, severity, device relatedness, start and stop times, duration, outcome, and any action (e.g., treatment/follow-up tests). The investigator must also assess whether the event meets the criteria for classification as an SAE.

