8.2 ANALYSIS POPULATIONS

For the purposes of analysis, the following analysis sets are defined in [Table 4](#) below.

TABLE 4. SUMMARY OF ANALYSIS SETS

Analysis Set	Description
Enrolled	All participants who signed the ICF
Intention-To-Treat (ITT)	All randomized participants with HAM-D6 measured at baseline. Participants will be included in the ITT population regardless of how often they engage with WB001 or ED001. This analysis set will be the primary set used for analyses/summaries of the primary efficacy endpoint, as well as for all secondary and exploratory efficacy endpoints.
Per-Protocol (PP)	All randomized participants also in the ITT population who complete 8 weeks of treatment and have at least 75% compliance on engaging with the Woebot application at least 1 day per week, and who have HAM-D measured at baseline, Week 4, and Week 8, with no other major protocol deviation that could affect the interpretability of the efficacy outcome. This analysis set will be used for sensitivity analyses.
Safety	All randomized participants who used WB001 or ED001 and who have at least one post-baseline safety assessment (i.e., C-SSRS). This analysis set will be used for summaries of safety data.

*Note: Inclusion criteria at screening will assess for participants engagement in TAU. If participant is confirmed as not having completed TAU by EOT, the data from these patients will be excluded from the primary analysis; however, their data will be retained for the purpose of conducting exploratory analysis.
	

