9.4 SAFETY ENDPOINT(S)

AEs and SAEs that may be reported by the participant or detected by the investigator through the C-SSRS will be compared between treatment groups. All safety variables will be summarized descriptively by randomized treatment.

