9.5 ANALYSIS OF SAFETY

The Safety Analysis Set will be used for the analysis of AE data.

AEs will be coded with MedDRA. All AEs with an onset date on or after the date of first use of the investigational product and before the date of last use of the investigational device will be collected and presented by system organ class and preferred term in frequency tables. Participants with multiple AEs will be counted only once within each preferred term and system organ class. Key participant information for participants with an AE with an outcome of death, participants with SAEs, and participants with an AE leading to withdrawal from the study will be listed.

Sponsor Name: Woebot Health

Protocol Number: WB001-001

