AE = adverse event; BL = baseline; CGI-I = Clinical Global Impression of Improvement; CGI-S = Clinical Global Impression of Severity; C-SSRS = Columbia-Suicide Severity Rating Scale; CSQ = Customer Satisfaction Questionnaire; EOT = end of treatment; EPDS = Edinburgh Postnatal Depression Scale; ET= Early Termination visit; GAD = Generalized Anxiety Disorder Questionnaire; HAM-D = Hamilton Depression rating scale; MIBS = Mother-to-Infant Bonding Scale; PHQ = Patient Health Questionnaire; PGI-C = Patient Global Impression of Improvement of Change; PGI-S = Patient Global Impression of Disease Severity; SCID-5-CT = Structured Clinical Interview for DSM-5 - Clinical Trials Version; Hybrid = indicates conducted in-person at BL and virtual by participant post-randomization through link; CIR = Central Independent Rater;

^a These assessments will be administered by blinded investigator or qualified designee (e.g., sub-investigator, or dually qualified site staff).

^b These assessments will be self-administered and completed independently by participant s as a link (± 3 days of visit date)

^c Will be administered by a CIR

^d Any confirmed Escalation trigger through the following three scenarios will result in PI-administered C-SSRS:

- [REDACTED]
- [REDACTED]
- [REDACTED]
- [REDACTED]
- [REDACTED]

^e Only includes modules for major depressive disorder (MDD), current and lifetime diagnosis of a psychotic disorder including postpartum psychosis and Schizophrenia, bipolar disorder, homicidal or infanticidal ideation, and history of drug and/or alcohol

AE/SAE collection will begin at the time ICF is signed. AEs/SAEs should be recorded until the EOT visit.

*Note: the HAM-D will be administered as the Structured Interview Guide for the Hamilton Depression Rating Scale – 17 item version (SIGH-D 17-item HAM-D) to derive the HAM-D6 as the primary endpoint

**Final Screening and Baseline visit assessments must be completed on the same day.

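### The Safety set requires a post-baseline C-SSRS, so an app user with a countable AE or SAE but no such C-SSRS is left out of the AE tables by arm

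*Combined protocol and SAP*

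**What the plan says.** Table 4 in Section 8.2 defines the Safety set as "All randomized participants who used WB001 or ED001 and who have at least one post-baseline safety assessment (i.e., C-SSRS", naming no other qualifying assessment. Section 9.5 states: "The Safety Analysis Set will be used for the analysis of AE data". It tabulates "All AEs with an onset date on or after the date of first use of the investigational product and before the date of last use", and plans listings with "Key participant information for participants with an AE with an outcome of death, participants with SAEs, and participants with an AE leading to withdrawal". Section 9.4 gives the purpose: "AEs and SAEs that may be reported by the participant or detected by the investigator through the C-SSRS will be compared between treatment groups".

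Section 5.3 and Appendix 3 schedule the C-SSRS at baseline, Week 4 (Day 28 ±3) and Week 8 (Day 56 ±3). AE capture does not depend on it. Section 7.3 says that "AEs and SAEs may be reported spontaneously by participants", and sets the period: "Reporting of non-serious AEs and SAEs will begin at the time of first interaction with the app and will continue through EOT". Section 4.7 foresees women who attend neither the Week 4 nor the Week 8 visit.

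**The concern.** The AE tables are meant to compare the arms on events during app use. Entry to them depends on a suicidality rating first scheduled four weeks in. A woman can use the app, have an AE recorded and still not qualify. Examples are death, withdrawal of consent to follow-up, or missing both visits, in each case without an interim C-SSRS. The ITT set in the same table has no comparable post-baseline requirement.

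Exclusion may also be related to the safety outcome. Section 4.6 makes an SAE of Grade 3 or higher a reason for discontinuation. The benefit/risk section describes withdrawal for worsening symptoms. Level 4 in Table 3 links withdrawal to events such as a suicide attempt. At stake are the published counts and rates by arm, most visibly for rare events.

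**Working it through.** The plan states no figure on this point, so there is nothing to reproduce. The check sets the passages side by side and then does the algebra.

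**1. Does any passage bring such a woman back into the tables?**
- Early-withdrawal visit (4.6): it carries the Week 8 assessments, but attendance is only encouraged. Discontinued women should keep attending visits unless they withdraw consent for follow-up.
- Unscheduled safety visit (5.3): C-SSRS only if needed.
- HAM-D or self-report flag (5.3): C-SSRS only if the investigator thinks it necessary.
- C-SSRS row of Appendix 3: given by the PI when a safety event is flagged and confirmed. What counts as a safety event is not defined.
- Appendix 3, footnote d: a confirmed escalation trigger leads to a C-SSRS. The scenarios are redacted.
- Section 9.4: summaries are by randomized treatment, which sets the grouping and not the population.

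Each C-SSRS provision brings some women back. None covers every recorded AE.

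**2. Formulas, per arm of n app users.** Let f = share with no post-baseline C-SSRS, and p_ret and p_exc = share with a recorded in-window AE among retained and excluded users.
- Women with an AE lost from the table = n × f × p_exc, never negative.
- Tabulated rate = p_ret.
- All-user recorded rate = (1 − f) × p_ret + f × p_exc.
- Tabulated minus all-user = f × (p_ret − p_exc), of either sign.

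**3. Illustration.** From the protocol: 210 planned, 1:1, so 105 per arm. Assumed, because the documents give no values: everyone used an app; f = 5%, 10% or 20%; p_ret = 10%. Over both arms, 210 × f = 10.5, 21 or 42 women leave the set. The table shows 10% throughout. All-user recorded rates, with tabulated minus all-user in points:

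| f | p_exc = 0% | p_exc = 10% | p_exc = 20% |
|---|---|---|---|
| 5% | 9.5% (+0.5) | 10.0% (0) | 10.5% (−0.5) |
| 10% | 9.0% (+1.0) | 10.0% (0) | 11.0% (−1.0) |
| 20% | 8.0% (+2.0) | 10.0% (0) | 12.0% (−2.0) |

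For f = 10% and p_exc = 20%: 0.9 × 10% + 0.1 × 20% = 11.0%, and 105 × 0.10 × 0.20 = 2.1 women with an AE are lost per arm.

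A wider assumed range, p_ret = 20%, p_exc = 5% to 60% and f = 5% to 20%, gives differences from 0.20 × (20 − 5) = +3.0 to 0.20 × (20 − 60) = −8.0 points. The loss runs from 105 × 0.05 × 0.05 = 0.3 to 105 × 0.20 × 0.60 = 12.6 women per arm.

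**4. Rare events.** Assume 3 women with an SAE among 105 users (2.9%) and 10 users without a post-baseline C-SSRS. If 0, 1, 2 or 3 of the three are among those 10, the table shows 3/95 (3.2%), 2/95 (2.1%), 1/95 (1.1%) or 0/95 (0%).

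**5. Between arms.** Assume 21/105 (20%) have an AE in each arm and 10 leave each set. If 5 of the 10 had an AE in one arm and 1 of the 10 in the other, the table shows 16/95 = 16.8% against 20/95 = 21.1%. That is an apparent gap of 4.2 points where the all-user recorded rates are equal.

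**The case against.** The best defence is that few women are affected. Each must have a recorded AE with onset before last use, yet no C-SSRS at Week 4, Week 8, early withdrawal, an unscheduled visit or escalation. An event that starts on or after the day use ends is lost through the Section 9.5 window, not through the set. The Appendix 3 rule for confirmed safety events would tend to bring in the women with events. The redacted triggers, or the detailed SAP that Section 8.1 says will expand on the methods and which is not in the text supplied, could shrink the gap further. All of this stands as a limit on size. It does not remove the gap, because a non-psychiatric AE gives no evident reason for a C-SSRS.

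A reader might infer three stronger things that the documents do not support:
- **That SAEs escape oversight.** Section 7.3 requires SAE reports to the sponsor within 24 hours and sends serious or related AEs to the DSMB, whatever the analysis set.
- **That the tabulated rates are known to be too low, or too high.** The formula compares two recorded rates. Women lost to follow-up may never have been questioned, so the all-user recorded rate is not the truth either; it counts them as AE-free.
- **That the listings of deaths, SAEs and AE withdrawals are certainly cut.** Section 9.5 opens by applying the Safety set to AE data, which suggests it, but does not say so for the listings.

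**Conclusion.** The concern holds as a possible loss of countable AEs and SAEs from the tables by arm. That counts can only be equal or lower follows from the definitions and needs no assumption. The size and sign of any difference in recorded rates are unknown. Every percentage above rests on assumed values of f, p_ret and p_exc, and the number of women affected may be small. Safety is summarised descriptively, so no formal test is at risk. Minor to should-fix, with medium confidence: the gap is plain in the text, but the full SAP and the trigger list could narrow it.

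**What to change.** In Table 4, define the Safety set as all randomized participants who used WB001 or ED001 at least once, with no post-baseline assessment required. In Section 9.5, state that this set is used for all AE and SAE tables and listings. Apply the post-baseline C-SSRS condition only to the C-SSRS summaries, and report by arm how many users had none.

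The cost is one sentence in Table 4 and one or two in Section 9.5, carried into the SAP, with no new data. The downside is that users never questioned after baseline enter the denominator and may dilute recorded AE rates. The AE and C-SSRS denominators will also differ and must be labelled.

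A separate point needs its own edit. Section 9.5 stops counting before the date of last use, whereas Section 7.3 continues reporting through EOT and Appendix 3 says "AEs/SAEs should be recorded until the EOT visit". Reconcile these passages, because the new set does not recover AEs with onset on or after last use.

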I agree to conduct this study according to this protocol and to comply with its requirements, participant to ethical and safety considerations and guidelines, and to conduct the study in accordance with the Declaration of Helsinki, International Council for Harmonisation guidelines on Good Clinical Practice, and applicable regional regulatory requirements.

I agree to comply with the procedures described for data recording and reporting and to permit monitoring and auditing by Woebot Health and inspection by the appropriate regulatory authorities.

I agree to make my participants' study records available to Woebot Health personnel, their representatives, and relevant regulatory authorities in order to verify data that I have entered the case report forms. I will retain the study-related essential documents until Woebot Health indicates that they are no longer needed. I am aware of my responsibilities as an investigator as provided by Woebot Health.

I understand that Woebot Health may decide to suspend or prematurely terminate the study at any time for whatever reason; such a decision will be communicated to me in writing. Conversely, should I decide to withdraw from execution of the study, I will communicate my intention immediately in writing to Woebot Health.

Investigator Name (Print)	Title
Institution:	
Signature:	Date

PROTOCOL SYNOPSIS

Sponsor Name: Woebot Health

Protocol Number: WB001-001

Protocol Number: WB001-001

Full Title: A Multicenter, Randomized, Double-Blind, Controlled Study Evaluating the Efficacy and Safety of a Digital Therapeutic WB001 as an Adjunct to Treatment as Usual Among Women with Mild to Moderate Postpartum Depression

Abbreviated Title: [Study Evaluating the Efficacy and Safety of WB001 as an Adjunct to TAU in Postpartum Depression]

Sponsor: Woebot Health

Coordinating Investigator: [TBA]

Study Type: Interventional

Planned Number of Subjects: 210, with interim analysis for sample size re-estimation

Study Sites: Up to 25 study centers within the U.S.

Primary Objectives: The purpose of the study is to determine whether, for women diagnosed with PPD, WB001 with adjunctive Treatment as Usual (TAU; WB001+TAU) can reduce symptoms of depression compared to an educational control with adjunctive TAU (Ed Control “ED001” +TAU), at the end of treatment (EOT; 8 weeks) as measured by the HAM-D6.

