- Must have current mild-moderate depression as measured by the HAM-D6 score > 7 and < 13 (i.e., between 8-12, inclusive) at screening (Bech et al., 2007; Pridmore et al., 2020)
- Participant must confirm having a form of TAU, defined as clinician supervised outpatient care management and includes follow-up visits, medication, psychotherapy, or some combination thereof
- As part of TAU during the study, any confirmed concomitant medications and/or psychotherapy are permissible and must be regularly scheduled or stable (dose and frequency) for over 4 weeks prior to baseline (BL) visit

Key Exclusion Criteria:

- Gestation less than 28 weeks
- HAM-D6 score ≤ 7 or ≥ 13 (severe depression) at Screening
- Currently pregnant or plans to become pregnant within the next 8 weeks
- History of drug and/or alcohol use disorder within the past 12 months measured by the SCID-5-CT (Williams JB, 2015)
- Lifetime history of suicide attempt or ideation with a plan and intent to harm oneself during the current episode of PPD
- Current or lifetime psychosis, including history of post- and peri-partum psychosis as measured by the SCID-5-CT (Williams JB, 2015)
- Current or lifetime history of schizophrenia, schizoaffective disorder, bipolar disorder, and/or homicidal or infanticidal ideation as measured by the SCID-5-CT (Williams JB, 2015)
- History of antidepressant treatment with ketamine/esketamine, electroconvulsive therapy, vagal nerve stimulation, or a deep brain stimulation device
- Fetal demise within the past 18 months
- Previous Woebot use

Study Conditions: 1:1 randomization to either [WB001+TAU] or [ED001+TAU]

Control Device: The educational control application is an educational app named ED001.

Sponsor Name: Woebot Health

Protocol Number: WB001-001

Treatment as Usual (TAU): Participants will receive TAU, which is clinician supervised outpatient care including follow-up visit(s), psychotropic medication, psychotherapy, or some combination thereof.

Primary Endpoint: Difference in HAM-D6 scores between groups at EOT, controlling for baseline (BL) and other covariates

Secondary Endpoints:

1. Difference between arms in the following assessments at EOT, controlling for BL and other covariates:

- Edinburgh Postnatal Depression Scale (EPDS)
- Maternal-Infant Bonding Scale (MIBS)
- Patient Health Questionnaire-9 (PHQ-9)
- Generalized Anxiety Disorder-7 (GAD-7)

2. Difference in HAM-D6 scores within arms between BL and EOT

Exploratory Endpoints:

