- Change from baseline in Clinical Global Impression-Improvement (CGI-I) the CGI-Severity (CGI-S) at Week 4 and Week 8
- Change from baseline in Patient Global Impression-Change (PGI-C) and Patient Global Impression-Severity (PGI-S) at Week 4 and Week 8
- Client Satisfaction Questionnaire-8 at Week 8

Safety Endpoints: C-SSRS and Adverse Events (AEs), Serious Adverse Events (SAEs)

Safety Aim: To evaluate the safety of [WB001+TAU] versus [ED001+TAU] based on PI and Sponsor determined AE and SAEs. The study will use the Columbia-Suicide Severity Rating Scale (C-SSRS), the PHQ-9 item #9, and the EPDS item #10, and the HAM-D17 item #3 to facilitate identification of AEs and SAEs. It would be separately determined whether identified AEs or SAEs are related to the device.

Statistical Methods: The primary efficacy endpoint is the difference between treatment arms in the HAM-D6 score at Visit Week 8 after controlling for baseline and other covariates. For the ITT population, a restricted maximum likelihood (REML) based linear MMRM approach will be used to test for systematic differences in change between arms over time, after accounting for participant-specific heterogeneity in HAM-D6 scores residual error structure. The MMRM will be parameterized to include random effects for site and repeated measures for post-baseline visits using an unstructured residual covariance structure (3 parameters); in the unlikely event that the unstructured covariance matrix fails to converge, the model will be refit with a first order autoregressive covariance matrix (2 parameters).

Sponsor Name: Woebot Health

Protocol Number: WB001-001

This test will be performed using the final, MMRM model-based t-test with a two-sided significance level of 5%. Estimated least squares means for change from baseline and the observed absolute values (\pm SE) at each visit by treatment group will be plotted over time.

No explicit imputation will be performed; the MMRM model described above will be run on this population, which implicitly imputes missing data under a missing at random (MAR) assumption.

As a sensitivity analysis for the primary analysis using ITT population, MMRM model in the same manner as described above will be conducted in the PP population.

The treatment effectiveness on MIBS, EPDS, PHQ-9, and GAD-7 (difference between arms at Week 8, controlling for baseline) will be evaluated using the same analysis plan proposed for the analysis of the primary endpoint (HAM-D6).

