Thus, for this study, the primary efficacy endpoint is the difference between treatment arms in the HAM-D6 score at Week 8 after controlling for baseline and other covariates. For the ITT population, a restricted maximum likelihood (REML) based linear mixed-effects model for repeated measures (MMRM)-approach will be used to test for systematic differences in change between arms over time, after accounting for participant -specific heterogeneity in HAM-D scores residual error structure. The MMRM will be parameterized to include random effects for site and repeated measures for post-baseline visits using an unstructured residual covariance structure (3 parameters); in the unlikely event that the unstructured covariance matrix fails to converge, the model will be refit with a first order autoregressive covariance matrix (2 parameters).

Sponsor Name: Woebot Health

Protocol Number: WB001-001

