9.9 INTERIM ANALYSIS

After 50% of the planned participants have completed the study (been evaluated after 8 weeks on treatment) an interim analysis will be conducted on blinded data by an independent statistician to verify that the effect size estimates used to plan the study sample remain reasonable and, if needed, calculate a new required sample given the updated effect size estimates. Specifically, the clinically important difference (CID) analyses (described in section 7.2 of the SAP) will be performed on the interim HAM-D6 data to determine whether clinician judgments of category differences in the HAM-D6 in the context of use of PPD (Δ) are consistent with a priori expectations of a 3-point CID for MDD. Additionally, the SD of the difference between baseline and Week 8 will be calculated to determine whether it is in line with expectations for detecting a 3-point (or Δ) difference between arms with $\alpha = .05$, two-tailed and $1-\beta = .80$, i.e., $n / \text{arm} \geq 2^*(z_{\alpha/2} + z_{1-\beta})^2 * \text{SD} / \Delta = 2^*2.8^2 * \text{SD} / \Delta = 15.68 * \text{SD} / \Delta$.

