APPENDIX 3: SCHEDULE OF EVENTS

Mechanism to Execute	Epochs	Screening/Baseline** Day 1 must be completed on same day	Week 4 Day 28 ±3	Week 8 (EOT/ET) Day 56 ±3
Clinical Outcome Assessments			Intervention Period	
In-person by site staff	Randomization *After the following assessments are completed and patient meets all I/E Criteria	X		
In-person by blinded site staff via tablet or paper copy	Informed Consent	X		
In-person by blinded site staff for input in EDC	Inclusion/Exclusion Criteria	X		
In-person by blinded site staff for input in EDC	Demographics	X		
In-person by blinded site staff for input in EDC	Previous Medications	X		
In-person by blinded site staff for input in EDC	Psychiatric History	X		
In-person by blinded site staff/PI via tablet	SCID-5-CT^{a, e}	X		
Hybrid by blinded site staff/PI for input in EDC	Concomitant Medications and Therapy *Post randomization, will rely on self-report from participant on continued TAU	X	X	X
Hybrid by blinded site staff/PI for input in EDC	Pregnancy History and Status *Post randomization, will rely on self-report from participant on pregnancy status	X	X	X
Virtual by blinded CIR	HAM-D17^c *Primary endpoint is HAM-D 6 derived from HAM-D17	X	X	X

Sponsor Name: Woebot Health

Protocol Number: WB001-001

Hybrid by blinded site staff/PI	C-SSRS^a *Safety endpoint and will be administered virtually by PI if safety event is flagged and confirmed	X	X	X
Self-report via link	EPDS^b *If safety flag is raised due to score of >2 on item #10, EPDS, PI/site staff are notified immediately for review, and action, if needed	X	X	X
Self-report via link	PHQ-9^b *If safety flag is raised due to score of ≥ 2 on item #9, PHQ-9PI/site staff are notified immediately for review and action	X	X	X
Self-report via link	GAD-7^b	X	X	X
Hybrid by blinded site staff/PI into EDC	CGI-S^a	X	X	X
Virtual by blinded site staff/PI into EDC	CGI-I^a		X	X
Self-report via link	PGI- S^b	X	X	X
Self-report via link	PGI- C^b		X	X
Self-report via link	MIBS^b	X	X	X
Self-report via link	Healthcare Utilization	X	X	X
Self-report via link	Program Assignment Assessment (Blinding)			X
Hybrid by blinded site staff/PI into EDC	AEs/SAEs Assessment^a *Includes confirming no recent hospitalizations for mental health-related incidence	X	X	X
Self-report via link	CSQ-8^b			X
Virtual by blinded PI	Escalation Trigger Follow-Up		X ^d	

Sponsor Name: Woebot Health

Protocol Number: WB001-001

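### A note under Table 4 drops participants who did not complete TAU from the primary analysis, contradicting the ITT definition and leaving a post-randomization subset open to bias

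*Combined protocol and SAP*

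**What the plan says.** Section 8.2, Table 4, defines the ITT set as "All randomized participants with HAM-D6 measured at baseline", keeps participants in it however little they use the app, and names it as the primary set for the primary endpoint. Section 9.1 opens its model description with "For the ITT population, a restricted maximum likelihood (REML) based linear mixed-effects model for repeated measures". Section 9.8 and the synopsis also place the primary MMRM on ITT.

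The note under Table 4 then states: "If participant is confirmed as not having completed TAU by EOT, the data from these patients will be excluded from the primary analysis". Data from these women are kept for exploratory use only.

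After randomization, according to the concomitant medications and therapy row of Appendix 3, the study "will rely on self-report from participant on continued TAU". TAU is described in the synopsis and section 4.1 as supervised outpatient care made up of visits, medication, psychotherapy or a mixture. No section says what it means to have completed it.

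**The concern.** A woman with a baseline HAM-D6 who stops TAU before Week 8 is in the primary analysis under the ITT row and out of it under the note. The note mentions screening, but its test is TAU status by end of treatment, so it cannot be read as removing only women who were ineligible at entry.

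Stopping TAU is a post-randomization event that may be related to both treatment and outcome. Women who improve may drop visits or therapy; women who disengage may drop everything. An app that delivers CBT could displace usual care more than an educational app does, or for different reasons. Conditioning on such an event gives up the protection of randomization.

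If stopping relates to outcome differently in the two arms, the Week 8 difference is biased, in either direction, and the 5% error rate is not kept. The result would still be labelled ITT. Section 9.2 applies the same analysis plan to the secondary endpoints, so the problem may carry over to them.

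**Working it through.** **Inputs from the plan.** The planned size is "210, with interim analysis for sample size re-estimation" (synopsis), randomized 1:1, so 105 per arm. The test is two-sided at 5% (synopsis, Statistical Methods). The target is 3 HAM-D6 points at Week 8 (8.3). Power of 0.80 appears in 9.9 for the interim re-estimation.

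**Inputs not in the plan (assumed here).** TAU-stopping rates, the outcome gap between those who stop and those who do not, and the SD.

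**The plan's own figure.** The 210 comes from simulations (8.3) whose SD and dropout inputs are not visible, so it can only be back-solved. With no dropout and 80% power, SD = 3 × √(105 / 15.70) = 7.76, where 15.70 = 2(1.960 + 0.842)². With 10% to 30% dropout the implied SD is 7.36 to 6.49.

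**Bias.** In one arm let q be the share excluded and d the mean HAM-D6 of the excluded minus that of the retained. The full-arm mean equals the retained mean + q·d, so exclusion shifts the arm mean by −q·d. The bias in the contrast WB001 minus ED001 is −(q_W·d_W − q_E·d_E). Absolute values are shown below.

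**Type I error.** With no true effect, SE = SD × √(1/n_W + 1/n_E), n = 105(1 − q), and type I error = P(|Z + bias/SE| > 1.96).

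Worked case: 20% v 5% excluded, 4-point gap in both arms, SD 5.
- n = 84 and 99.75; bias = (0.20 − 0.05) × 4 = 0.60.
- SE = 5 × √(1/84 + 1/99.75) = 0.740; bias/SE = 0.81; type I error = 0.128.

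| Excluded (one arm v other) | Gap | Bias (points) | Type I error |
|---|---|---|---|
| 15% v 15% | 3, same direction | 0 | 0.050 at any SD |
| 10% v 5% | 3, same direction | 0.15 | 0.053 to 0.058 (SD 6 to 4) |
| 20% v 10% | 3, same direction | 0.30 | 0.079 / 0.069 / 0.058 at SD 4 / 5 / 7.76 |
| 20% v 5% | 4, same direction | 0.60 | 0.173 / 0.128 / 0.104 at SD 4 / 5 / 6 |
| 10% v 10% | 4, opposite directions | 0.80 | 0.196 at SD 5 |
| 15% v 15% | 3, opposite directions | 0.90 | 0.324 / 0.225 / 0.121 at SD 4 / 5 / 7.76 |

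**Simulation check** (SD 5, 20,000 trials per scenario, 3-point gaps). The retained subset gave 0.051 for 15% v 15% same direction, 0.068 for 20% v 10%, and 0.230 for 15% v 15% opposite directions. With all 210 kept, type I error was 0.048 to 0.052 over these scenarios and a fourth (20% v 20%, opposite directions).

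**Power.** At SD 7.76, excluding 10%, 20% or 30% in both arms leaves 189, 168 or 147 participants, and power falls from 80% to 75.7%, 70.7% or 65.0%.

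**Does another provision repair it?** MMRM under missing at random does not, because the note removes a participant's data instead of treating some values as missing. The per-protocol analysis is narrower than ITT. The multiple imputation in 9.8 is for missing values. None is described as restoring the excluded women. Replacing withdrawn participants (4.6) may restore the number, not the randomized comparison.

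**The case against.** The strongest reply is about size.

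- **The excluded fraction may be small.** TAU is defined broadly, every participant must confirm it at entry, any medication or psychotherapy must already be stable for over 4 weeks, and treatment lasts only 8 weeks. The note reaches only those confirmed as not completing; nothing makes a change of dose or frequency grounds for exclusion. This stands: nothing in the plan supports 20% over 2%. Nothing rules 20% out either.
- **The larger figures need strong assumptions.** A fourfold difference in exclusion between blinded arms with a 4-point gap is a severe case. At the back-solved SDs of 6.49 to 7.76 it gives a type I error of about 8% to 10%, and the mild case is close to nominal. This stands, and the figures are illustrations.
- **Blinding limits selective exclusion.** Participants and raters are blinded (3.5), and analysts stay blinded until database lock and identification of deviations (8.1). Section 5.1 adds that therapy changes are to be confirmed. This guards against exclusions chosen with knowledge of the arm. It does not stop participants' own behaviour from differing by arm.
- **The sponsor may want the effect in women who remain on TAU,** since section 2 frames the app as adjunctive. That is a legitimate question, but dropping non-completers does not validly estimate it.
- **The SAP may settle the point.** Sections 8.1 and 9.9 refer to a SAP whose text was not available to me. If it does settle the point, the protocol would still contradict itself.

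None of this reconciles the note with the ITT row.

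**Conclusion.** The concern holds. As written, the protocol gives two incompatible rules for who is in the primary analysis. Following the note replaces the stated ITT comparison with a subset selected on a largely self-reported event after randomization.

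Bias is possible, not certain. It is zero when exclusion rates and the prognosis of those excluded match across arms. Otherwise it can favour either arm, and equal rates do not protect if the reasons for stopping differ. On the assumed values it ranges from 0.15 points, with type I error barely above 5%, through 0.6 points (20% of the 3-point target) with type I error of 10% to 17% at SD 4 to 6, up to 0.9 points when the arms lose opposite kinds of patient. All these sizes rest on assumed rates, gaps and SDs. The contradiction does not, and it must be fixed before unblinding.

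**What to change.** 1. Delete the exclusion in the note under Table 4. State that every ITT participant enters the primary MMRM whatever happens to TAU after randomization.
2. Name TAU change or cessation as an intercurrent event handled by a treatment-policy strategy.
3. Keep the restriction to women who completed TAU only as a supplementary analysis, labelled as a non-randomized comparison, and define completion objectively; without a definition it cannot be run reproducibly.
4. Check that the SAP states the same primary set.

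The cost is wording in section 8.2, and in the SAP if it repeats the exclusion. TAU changes are already recorded at Weeks 4 and 8, so no new data are needed. The estimated effect may be slightly diluted if some women stop TAU. In return there is no TAU-driven loss of sample size, and the primary result can properly be called ITT.
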